5.2.13 Safety Evaluation

Subject safety will be monitored by adverse events, vital signs, physical examinations, and laboratory data (Appendices 2 and 8). Interruption of intervention will be considered in consultation with the study team and the clinical care providers (Appendices 9, 10, 11, 12).

5.2.14 Administration of Study Drug

Study drug will be administered as described in Section 4, and in Appendices 3 and 4, of the protocol.

5.2.15 Medical Record Review

Include a listing of the variables that will be abstracted from the medical chart (paper or electronic).

Date of birth Date of symptom onset Symptom complex at symptom onset Date of diagnosis Genotype MRI and CT findings Weight Height Head circumference Prior health events Prior and concomitant medications Level of baseline neurologic function (rolling, sitting, ambulation, speech etc).

5.2.16 Pregnancy Testing

A pregnancy test will be performed (if applicable).

5.2.17 Pharmacokinetic Evaluation

Samples for Drug Concentration Measurements Pharmacokinetics Venous blood samples for the measurement of baricitinib concentrations will be collected from all patients enrolled in the study. Samples will be collected after beginning baricitinib therapy and at each dose increase at the time points shown in the Study timeline and may be collected at each study visit with blood sampling for safety monitoring. In these cases, PK sampling will occur at least 72 hours after dosing changes or at the next visit.

PK testing may include a single measurement at 1.5 hours, or a full PK series at baseline, 1.0 hours, 1.5 hours and 4 hours post dose, and may include several doses during the day (eg morning and afternoon dose). For PK series, an IV will be placed.

For single PKs, these will be drawn with the safety laboratory monitoring. PK samples may be banked for later analysis.

If a patient has an adequate response to treatment at a lower dose than the maximum dose, but becomes unresponsive at a later time, the schedule of dose increases and PK sampling can be resumed. If a patient's daily dose is divided into multiple doses, an additional PK sample may be collected pre-dose for each additional dose. For all PK samples taken, the actual date and exact timing (24-hour clock) of PK sample collection and the date and time of the last 2 doses prior to the PK sample should be recorded. Plasma samples will be kept frozen at approximately –20° C to –80° C until the time of the assay. The assay may be performed at a later time. Samples will be kept in storage at a laboratory facility designated by the Sponsor. If the blood volumes required for PK sampling exceed established local guidelines for phlebotomy, then the PK sample collection may be modified.

5.2.18 IFN Signaling Gene Score

IFN scores are based on mRNA expression of IFN signaling genes (ISG) and represent a surrogate marker for autoinflammation in a variety of disorders ³⁹⁻⁴¹. IFN scores based on mRNA expression of ISGs have been used to assign a severity score of autoinflammation in a variety of disorders, including AGS⁴ and systemic lupus ervthematous ^{39,40}. We will measure ISG in individuals affected by AGS as per established protocol ^{4,42,43}. ISG scores will be calculated for all AGS affected individuals in the MDBP registry with available blood samples (180 AGS samples and 104 control samples) as per established methodology ^{4,42-44}. In brief, copy number of mRNA transcripts of the six type I IFN-inducible genes (IFI27, IFI44L, IFIT1, ISG15, RSAD2, and SIGLEC1)⁴ and four housekeeping genes (ALAS1, HPRT1, TBP, and TUBB) are quantified using Nanostring nCounter[™] Digital Analyzer. The raw copy number of mRNA transcripts of each type I IFN-inducible gene is standardized (stdGene) using the geometric mean of the four housekeeping genes for each individual. The six-gene IFN signature in each individual is calculated using the median of the Z scores. The IFN signature is considered positive (IFN high) if the value is ≥1.96 (>98centile) (one tail analysis). This test is a research test performed in a non CLIA approved laboratory, and will not be used to make clinical decisions around enrollment or patient management.

5.2.19 Leftover Samples for Future Research

Samples obtained during the course of this research project that represent leftover biological samples, will be stored by the sponsor and analyzed in the future, based on scientific questions that may arise during the course of the project.

6 STATISTICAL CONSIDERATIONS

6.1 Primary Endpoint

The primary endpoint will be the change in the AGS scale from baseline to 52 weeks.

6.2 Secondary Endpoints

Secondary endpoints will include the following:

- Improvement of the AGS scale from Screening to Treatment over time.
- Improvement of the GMFM-88 between Screening and Treatment over time.
- The change in Interferon Signaling gene score between Screening and Treatment over time.
- The change in skin symptoms between Screening and Treatment over time using the CLASI.
- Safety and tolerability of DRUG based on Adverse Events (including laboratory abnormalities).
- Change in AGS disease severity score (daily diary) between Screening and two years of treatment.

6.3 Statistical Methods

6.3.1 Baseline Data and Descriptive Analysis

Baseline and demographic characteristics will be summarized overall by standard descriptive summaries (e.g. means and standard deviations for continuous variables such as age and percentages for categorical variables such as gender). In addition, demographic characteristics and clinical variables that are evaluated at the first encounter will be compared between subjects who are never treated, versus those who are eventually treated. Patients are not randomized to receive treatment (or not), so it is important to identify variables that are associated with an increased (or decreased) likelihood of receiving treatment. Chi-square tests will be used to compare categorical variables between groups. T-tests or tests of medians (for skewed variables) will be used to compare continuous variables between groups. Overlaid histograms will also be used to evaluate the distribution of continuous baseline variables between patients who were never treated, versus those who were eventually treated. In addition, Kaplan-Meier analysis with the log rank test will be used to compare the distribution of time to treatment between levels of categorical variables (e.g. group genotype) measured at baseline. In our preliminary analysis, we did not identify meaningful differences between patients who were never treated, versus those who were eventually treated.

We will conduct descriptive statistical analysis using inferential and graphical secondary data analytic techniques. The primary and secondary assessments will first be summarized by time of measurement. In addition, individual "spaghetti" plots will be generated for each assessment. Changes in primary and secondary outcomes from baseline (with 95% confidence intervals [CI]) will be calculated at specified time points, e.g. between baseline and 52 weeks. In addition, overall changes (final minus baseline) (with 95% CI) will be computed for primary and secondary outcomes. In addition to means (with 95% CI) we will also calculate median changes (with 25th to 75th

percentiles). Analyses will be conducted in Stata 18.0, with a p-value < 0.05 as the criterion for statistical significance.

6.3.2 Primary Outcome Analysis

As is often the case in a study of a rare disease, we face a number of challenges in our analysis. The number of available patients with AGS is limited, so that our sample size is small. This protocol grew out of a compassionate use trial, so that randomization could not be employed to assign patients to receive treatment (or not). The temporal spacing of measurements differs between treated patients versus historical controls. As a result of these features, there are limitations to many of the standard statistical approaches. Our approach will therefore be to apply a recommended approach for efficacy, but to also apply several sensitivity analyses. Our goal will be to demonstrate efficacy for several statistical approaches, as we achieved in our analysis of preliminary data.

Our efficacy analysis for our primary outcome will apply the method described in Section 15.4 of Fitzmaurice, Laird, & Ware⁷⁴ that decomposes longitudinal effects of treatment versus cross-sectional effects due to participants starting treatment at different ages. We will first create a time for each patient that is negative prior to treatment and is positive after treatment. We will then fit a GEE model that includes time within patients, an indicator variable for treatment and a time by treatment interaction term. If the interaction term is significant, this will indicate that the change over time in AGS score (slope) is different after treatment, versus before. If the interaction term is not significant, it will be removed and the model will be fitted with time and the indicator variable for (post) treatment. If the indicator variable differs significantly from zero, this will indicate that the AGS score is higher on average, post-treatment. To compare values at baseline and 52 weeks post baseline, different parameterizations of time (continuous versus indicator variables at different visits) will be considered and analyses will also be performed on data restricted to values measured at baseline and 52 weeks post baseline. This approach will first be applied to patients who are eventually treated. to compare their AGS scores pre versus post-treatment.

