Statistical Considerations (sample size and analysis plan):	The change over time in AGS scale will be compared pre and post treatment with a GEE analysis that accounts for age at treatment initiation. Sensitivity analyses will also be performed, to evaluate the efficacy of treatment across several statistical approaches with varying assumptions. Sample size considerations were based on preliminary data. In preliminary data, the average of within subject changes (post-treatment average minus pre-treatment average) was 0.80 with a standard deviation of changes of 1.04. This corresponds to an effect-size of 0.80/1.04 = 0.77. From PASS 16, a sample size of 30 data pairs achieves 98.3% power to reject the null hypothesis of zero effect size when the population effect size is 0.77 and the significance level (alpha) is 0.050 using a two-sided paired t-test. Should the effect- size be smaller than we observed in our preliminary data, we will have 80% power to detect an effect size of 0.53, which corresponds to an average of within subject changes of 0.55, if the SD of changes is 1.04.
Funding Sponsors (federal, state, foundation and industry support):	Drug and grant support provided as a donation by Eli-Lilly Secondary funder: Pennsylvania Department of Health

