6.3.3.2 Analysis of the GMFM-88

In addition, we will perform a secondary analysis of the GMFM-88 based on the cohort designation in AGS subjects based on their baseline AGS scale. As described earlier, the AGS scale is simple enough to be able to be applied retrospectively, based on clinical notes; this allowed us to develop a historical control cohort for comparison. Based on our pilot data, we have defined three cohorts for this study (Table 3) according to baseline neurologic function as measured by the AGS scale. The more severely affected individuals, due to floor effect, will use the AGS scale as a primary

outcome measure. Individuals with baseline AGS scales of \geq 9 have measurable function on the GMFM-88 and other functional assessments and this can be applied to this population.

Changes in GMFM-88 will first be compared between AGS cohorts descriptively, including graphical displays (e.g. overlaid lowess curves for each outcome versus treatment day, by cohort). GEE models will be fitted that model change in outcome over time; these models will include indicator variables for cohorts B and C (with cohort A as reference) and time by cohort interaction terms. Different parameterizations of time will be considered and the fit of models will be compared using goodness of fit criteria for GEE.

 Table 3. Cohort designation in AGS subjects based on baseline AGS scale.

AGS cohort				
Α.	AGS scale 0-3			
В.	AGS scale 4-8			
С.	AGS scale 9-11			

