6.4 Sample Size and Power

Sample size calculations were performed using PASS 16 sample size software and were based on preliminary data in 35 patients with available data on the AGS scale.

Analysis of the primary outcome, safety data including laboratory studies and adverse events, will be descriptive and include all individuals, available studies and AEs. Power

analysis is not possible for these analyses, since adverse events may be rare, even in the AGS population, and statistical comparisons may not be feasible.

We anticipate that we will have an evaluable sample size of ~45 treated patients. For the analysis of secondary outcomes, in our preliminary analysis when we compared the average of AGS scales prior to treatment (pre-treatment average) to the average of the AGS scale after treatment (post-treatment average), we observed that the average of within subject changes (post-treatment average minus pre-treatment average) was 0.80 (95% CI = 0.45, 1.16) and that the standard deviation of changes was 1.04. This corresponds to an effect-size of 0.80/1.04 = 0.77. From PASS 16, a sample size of 30 data pairs achieves 98.3% power to reject the null hypothesis of zero effect size when the population effect size is 0.77 and the significance level (alpha) is 0.050 using a twosided paired t-test. Should the effect-size be smaller than we observed in our preliminary data, we will have 80% power to detect an effect size of 0.53, which would correspond to an average of within subject changes of 0.55, if the SD of changes is 1.04. We will therefore have sufficient power to detect differences that are similar to those observed in preliminary data. For the more complex analyses that are proposed for the larger data set that contains the historical controls (>50), our power will be even greater.

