Drop-Out: Overall, this clinical study may enroll up to 55 patients. However, power analysis suggest that an enrollment number of up to approximately 30 is required to obtain results for efficacy that are clinically meaningful, and accounting for those subjects who are found to be ineligible at screening, subjects withdrawn from participation for various reasons and those who are enrolled to this study who are not initially eligible at screening. In addition, some participants may be lost to follow up, or may not survive until one-year post-baseline, when the primary efficacy analysis will be conducted. Thus, we expect to be able to perform the necessary analysis even if there is significant drop out.

We will evaluate the reasons for drop-out carefully, especially with respect to the missing at random assumption that is required for GEE/QLS regression. As described above, a sample size of 30 patients will be adequate for analysis of our primary outcome. The goal of the secondary analyses will be primarily to inform the generation of hypotheses for future studies in this population.

The analysis of data obtained from this group of initially ineligible, but prospectively approved subjects entered to the study, will be assessed independently of the main group of subjects who meet all eligibility criteria. The statistical analysis within this group will depend on the total number of subjects in the group, as well as the degree of clinical heterogeneity of these patients. If the sample size is large enough we will attempt to replicate the analyses that are performed for the eligible participants in this group.

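### The GEE tests are judged at p<0.05 with about 30–45 treated patients, but no variance estimator, reference distribution or small-sample correction is named; an uncorrected robust z test would run at about 6–8% in the primary model, not 5%

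*Combined protocol and SAP*

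**What the plan says.** Section 6.3.2 defines the primary efficacy model: "We will then fit a GEE model that includes time within patients, an indicator variable for treatment and a time by treatment interaction term". The interaction is tested first. If it is not significant it is dropped, and the treatment indicator is tested instead. The model is applied first to patients who are eventually treated. Section 6.3.1 gives the decision rule: "Analyses will be conducted in Stata 18.0, with a p-value < 0.05 as the criterion for statistical significance".

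Section 6.3.3.1 repeats the GEE with historical controls added, allows QLS as a companion method, and selects the working correlation by goodness of fit. For GMFM-88, Section 6.3.3.2 says that "these models will include indicator variables for cohorts B and C (with cohort A as reference) and time by cohort interaction terms".

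On numbers, Section 6.4 says "We anticipate that we will have an evaluable sample size of ~45 treated patients" and that "a sample size of 30 patients will be adequate for analysis of our primary outcome". The power calculation is for a different test; the Protocol Synopsis states that "the significance level (alpha) is 0.050 using a two-sided paired t-test".

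None of these sections names a GEE variance estimator, a reference distribution or a small-sample correction. Section 6.3.2 does acknowledge that the sample is small. Its answer is a set of sensitivity analyses.

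**The concern.** The robust (sandwich) variance used with GEE is biased downwards when there are few clusters, and a z reference ignores the uncertainty in that variance. Both faults make p-values too small and confidence intervals too narrow. The bias grows when a few patients carry much of the information, for example late-treated children with long pre-treatment histories, and when a coefficient depends on a small subgroup.

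Model-based standard errors do not avoid the problem, because they are valid only if the working correlation is right. As written, two analysts could follow the plan and report materially different p-values for the primary test. In an open-label, non-randomised trial, the nominal 5% level of the main efficacy test ought at least to be close to 5%.

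**Working it through.** **1. The plan's own figure.** Inputs from Section 6.4: mean change 0.80, SD 1.04, n = 30 pairs. "This corresponds to an effect-size of 0.80/1.04 = 0.77". Noncentral-t power for a two-sided 0.05 paired t-test, with 29 df and noncentrality 0.77 × √30 = 4.22, is 98.3%. This agrees with "a sample size of 30 data pairs achieves 98.3% power to reject the null hypothesis of zero effect size". The effect size with 80% power is 0.529, and 0.529 × 1.04 = 0.55, also as stated. The figure is correct, but it describes a paired t-test; the plan states no error rate for the GEE tests.

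**2. Cluster counts.**
- Primary model: 30 (called adequate) to about 45 (expected), from Section 6.4.
- Models with controls: more than 50 added (Section 6.4), so 30 + 50 = 80 to 45 + 50 = 95 or more.
- Cohorts: Section 1.5 reports pilot groups of 19, 6 and 9 out of 34. Scaled to 45: A 19/34 × 45 = 25, B 6/34 × 45 = 7.9, C 9/34 × 45 = 11.9. Scaled to 30, cohort B is 5.3. These expected counts are derived; the plan does not give them.

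**3. Closed form for the simplest case** (one mean change per patient, uncorrected variance, z cut-off 1.96). With divisor n, the true error is P(|t| on n−1 df > 1.96 × √((n−1)/n)). With divisor n−1, it is P(|t| on n−1 df > 1.96).

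| n | cut-off, divisor n | error, divisor n | error, divisor n−1 |
|---|---|---|---|
| 45 | 1.938 | 5.9% | 5.6% |
| 30 | 1.927 | 6.4% | 6.0% |
| 12 | 1.877 | 8.7% | 7.6% |
| 8 | 1.833 | 10.9% | 9.1% |
| 6 | 1.789 | 13.4% | 10.7% |

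**4. Null simulations of the planned models.** Gaussian GEE, uncorrected sandwich, z reference, 1,000–3,000 datasets per scenario, Monte Carlo error about 1–2 points. Visit times, random slopes and variances are assumptions. The corrected comparator is the Mancl-DeRouen variance with a t reference.

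*Primary model, near-balanced or moderately uneven follow-up.* At n = 30 the interaction test ran at 6.9–8.7% (the top value with a discrete scale) and the treatment indicator at 6.2–7.4%. At n = 45 the figures were 5.7–6.9% and 5.7–6.6%. Corrected: 3.9–5.3%.

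*Primary model, strongly uneven follow-up.* Assumed: age at start lognormal with median 3 years (range 0.2–15), 1–6 pre-treatment and 4 post-treatment scores, residual SD 0.5, slope SD 0.15–0.3 per year.

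| n | test | uncorrected | corrected |
|---|---|---|---|
| 45 | indicator | 9.9–12.9% | 6.0–6.5% |
| 45 | interaction | 7.0–8.6% | 4.7–5.5% |
| 30 | indicator | 13.1–15.3% | 5.6–6.8% |
| 30 | interaction | 7.5–9.3% | 4.4–4.5% |

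*Sensitivity to those assumptions at n = 45* (indicator / interaction, uncorrected). Slope SD 0.1: 8.2% / 6.1%. Pre-treatment window capped at 2 years: 6.5% / 4.8%. Balanced: 5.9% / 5.7%.

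*Model-based standard errors, primary model.* About 1.5% under working independence, and about 4–30% under exchangeable correlation, depending on follow-up and on the coefficient.

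*With historical controls* (interaction test). 30 + 50: 6.1%. 45 + 50: 7.3%.

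*GMFM-88, cohorts 25/8/12.* B-by-time 13.4–14.2% and C-by-time 10.2–11.0%, against 3.6–4.2% when corrected with t on (cohort size − 1) df. A separate run gave 10.6% for B-by-time, falling to 7.0%. With 5–6 patients in cohort B, 16–20% uncorrected and 1.5–3.0% corrected.

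**The case against.** A reader might infer that every GEE test in the plan runs at 9–12%. The documents do not support that, for four reasons.

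- Not every GEE model has only 30–45 clusters. The secondary AGS-scale models add more than 50 controls and run at about 6–7%.
- Double-digit rates for the primary test need a wide spread of ages at start and large slope variation. Section 6.3.2 says patients start at different ages but gives no spread, and its remark on differing spacing contrasts treated patients with historical controls. The analysis restricted to baseline and 52 weeks, which is closest to the endpoint in Section 6.1, is a balanced two-point design: 5.6–5.9% at n = 45 and 6.0–6.4% at n = 30.
- The cohort-B figures belong to a GMFM-88 analysis that begins descriptively. Section 6.4 describes secondary analyses as mainly hypothesis-generating.
- The robust z test is itself an assumption; the plan names no estimator.

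All four stand and limit the size of the point. It is also fair that Table 2 in Section 6.3.3.1 includes a paired t-test and a Wilcoxon signed-rank test. These support the overall reading, but they are sensitivity analyses. The GEE is the declared efficacy analysis, and its p-value remains uncorrected.

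The remedy is also not complete. Some excess can remain for the indicator under very uneven follow-up: one corrected run left 7.3% and another scenario 8.9%. Counting either step of the two-step rule as success gives 11.8–15.5% uncorrected and still 7–10% corrected. Most of that excess comes from having two chances at 0.05, which is a separate issue.

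**Conclusion.** The omission is real and affects the primary analysis, but its expected size is modest. If the unstated method is an uncorrected robust z test, the primary tests run at about 6–8% under near-balanced or moderately uneven follow-up. The treatment indicator reaches about 10–15% only under strongly uneven pre-treatment follow-up with widely varying slopes, and whether that applies cannot be told from the documents. If the method is model-based, the error could be much further off in either direction, about 2–30%, so leaving the estimator unnamed is itself a substantial part of the problem. Cohort-B-by-time tests run at about 9–14% with about 8 patients, in a secondary, hypothesis-generating model. All simulated rates depend on assumed visit patterns and variances and carry a Monte Carlo error of about 1–2 points.

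**What to change.** State in Sections 6.3.2 and 6.3.3, for GEE and QLS alike, that inference uses a robust variance with a named small-sample correction (for example Mancl-DeRouen or Kauermann-Carroll) and a t reference, and give the degrees-of-freedom rule. The alternative is to fit the same mean models by REML with random slopes and Kenward-Roger degrees of freedom; that route was not simulated here. Confirm before the SAP is fixed that the chosen software provides the option.

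With the Mancl-DeRouen variance and a t reference, most primary-model scenarios come to about 4–6%. The cost is SAP wording, a software option and slightly wider intervals. Tests in very small cohorts become conservative: with 5–6 patients in cohort B the corrected rate was 1.5–3.0%, so those GMFM-88 results are better presented as estimates with intervals than as tests. No new data are needed.

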6.3.3 Secondary Outcome Analysis

6.3.3.1 Longitudinal analysis of the AGS scale

In secondary analysis, we will include historical controls in the GEE models described in section 6.3.2; the "age at treatment" (time zero) for controls will be their age at their final encounter. The GEE models will also adjust for confounders (e.g. age of the subject, length of disease, and genotype⁷⁵) especially variables that were identified as being related to receiving treatment (see Section 6.3.1). We will fit several working correlation structures to model the association between the repeated measurements on each patient, and will use goodness of fit criteria for GEE to choose between the structures. Goodness of fit criteria will also be used to compare fit of models (e.g. for models that include time as a continuous variable versus a series of indicator variables for visit).

In addition to GEE, we will fit quasi-least squares (QLS) regression models.⁷⁶ QLS is a computational approach for estimation of the correlation parameters in the framework of GEE that can be applied should GEE fail to converge, or to fit correlation structures that are not available in the framework of GEE. For example, the Markov correlation structure that is plausible for unequally spaced data is not available in the **xtgee** command for implemention of GEE in Stata.

In addition to the GEE analysis that includes historical controls, we will implement several sensitivity analyses that are described in the Table below. These methods were successfully implemented in analysis of our preliminary data.

Table 2. Statistical Approaches				
Question to be Evaluated in Sensitivity Analysis	Statistical Approach			
For each patient who was eventually treated, if we obtain their average of their AGS scale values prior to treatment (pre-treatment average) and the average of their AGS scale values after treatment (post- treatment average), are the post-treatment averages higher than the pre-treatment averages?	Compute the average of the within subject changes (post-treatment average minus pre-treatment average) with 95% CI; apply the paired t-test to compare the mean of pre-treatment to the mean of post-treatment averages within patients.			

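### The primary endpoint is the week-52 change in the AGS scale, but 6.3.2 tests slope and then level, names no deciding week-52 test, and relies on power calculated for a sensitivity t-test

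*Combined protocol and SAP*

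**What the plan says.** Section 6.1: "The primary endpoint will be the change in the AGS scale from baseline to 52 weeks". The synopsis and 2.1 agree. The Drop-Out text in 6.4 places the main efficacy analysis at one year, noting that some participants "may not survive until one-year post-baseline, when the primary efficacy analysis will be conducted".

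Section 6.3.2 names one GEE as the efficacy analysis for this outcome, fitted first in patients who are eventually treated. It contains time (negative before treatment, positive after), a treatment indicator and their interaction. A significant interaction is read as a change in slope. Otherwise, "If the interaction term is not significant, it will be removed and the model will be fitted with time and the indicator variable", and a significant indicator is read as a higher average level after treatment. Section 6.3.1 sets p below 0.05 "as the criterion for statistical significance". No adjustment across the two steps is stated.

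The same section then turns to week 52. The coding of time is left open there: "different parameterizations of time (continuous versus indicator variables at different visits) will be considered". A two-visit version is planned as an addition to the main model: "analyses will also be performed on data restricted to values measured at baseline and 52 weeks post baseline". The section's stated aim is broad: "Our goal will be to demonstrate efficacy for several statistical approaches".

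The synopsis and 6.4 give 98.3% power with 30 pairs, and 80% power for an effect size of 0.53, for a two-sided paired t-test on post-treatment minus pre-treatment averages. That test is the first row of Table 2 (6.3.3.1), under the column head "Question to be Evaluated in Sensitivity Analysis". Section 6.4 introduces it under secondary outcomes, then treats 30 patients as enough for the primary outcome. Section 6.4 also attaches the primary-outcome label to the safety data, which 6.2 lists among the secondary endpoints.

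**The concern.** Three different quantities could answer the primary question: a change in slope, a change in average level, and a change at week 52. They can disagree, and the plan does not say which prevails. The trial is open-label and has no randomised control, so settling this after the results are seen is an avoidable source of bias.

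Two consequences follow. If a significant result at either GEE step counts as efficacy, the 5% error rate does not hold. And a reader of the synopsis or 6.4 will take 98.3% as the power of the primary analysis, when it belongs to another test of another quantity.

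**Working it through.** **1. The plan's own power figure.** Inputs from 6.4: mean change in averages 0.80, SD 1.04, n = 30, two-sided alpha 0.05. Effect size = 0.80/1.04 = 0.77. Paired t-test power comes from the noncentral t with n − 1 degrees of freedom and noncentrality d√n = 0.77 × √30 = 4.22. Result: 98.3%, as stated. The effect size giving 80% power is 0.529, and 0.529 × 1.04 = 0.55 points, as stated. At the roughly 45 evaluable patients that 6.4 expects, the figures are 99.9% and 0.427 (0.44 points). The arithmetic is right for that test.

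**2. Power for the week-52 change.** The documents give no SD for it, so the SD below is assumed. Same formula, two-sided 5%:

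| Assumed SD | 0.80 points, n=30 / n=45 | 0.55 points, n=30 / n=45 |
|---|---|---|
| 1.04 | 98.3% / 99.9% | 79.9% / 93.4% |
| 1.25 | 92.3% / 98.7% | 64.4% / 82.3% |
| 1.5 | 80.6% / 93.8% | 49.3% / 67.2% |
| 2.0 | 56.3% / 74.7% | 30.8% / 43.8% |

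For 0.80 points, power stays at 80% or more up to SD 0.80/0.529 = 1.51 (n=30) or 0.80/0.427 = 1.87 (n=45). These figures are for a simple paired change. A trend-adjusted contrast needs its own SD.

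**3. Error of slope-then-level.** Reference for two independent 5% tests: 1 − 0.95² = 9.75%. Simulation with no treatment effect: 16 scenarios of 4,000 trials, n = 30 or 45. AGS values fell at 3, 6, 9 and 12 months (5.2.4) or at 6 and 12 months (Appendix 2, footnote s). Assumed: 2, or 2 to 5, pre-treatment values including baseline; intercept SD 3; slope SD 0 or 0.25 per year; residual SD 0.7; unbounded scale; complete data; exchangeable correlation.

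- Either step significant, Mancl-DeRouen corrected SE with t reference: 8.5%–10.0% two-sided; 4.0%–4.9% in the favourable direction (nominal 2.5%).
- Each step alone, corrected SE: slope 4.1%–5.0%, level 4.2%–5.5%. The excess therefore comes from the two-step rule.
- Uncorrected robust SE with z reference: 11.0%–13.7%.
- Week-52 paired test allowed as a third route, corrected SE: 11.4%–13.4%.
- Remedies, corrected SE: 0.025 per step gives 4.0%–5.0%; one joint test gives 4.6%–5.7%.

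A second simulation (independence working correlation, uncorrected SE, 3 pre- and 4 post-treatment visits, residual SD 0.8) gave 10.7%–11.7% for slope-then-level.

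**4. Would a raw week-52 change be a safe deciding test?** With no drug effect and a natural gain g per year, the noncentrality is (g/SD)√n. For g = 0.25 and n = 30 it runs from 0.25/1.5 × √30 = 0.91 to 0.25/0.8 × √30 = 1.71. Chance of a significant favourable result, SD 1.5 to 0.8:

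| Assumed gain per year | n=30 | n=45 |
|---|---|---|
| 0.1 | 5%–10% | 6%–13% |
| 0.25 | 14%–38% | 19%–54% |
| 0.5 | 42%–91% | 59%–98% |

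In the second simulation, with a common trend of 0.5 points per year and slope SD 0.5, the raw test rejected in 58% (n=30) and 76% (n=45) of trials, against 11% for slope-then-level. The GEE keeps time in the model; the raw change does not.

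**The case against.** The plan has more structure than a quick reading suggests. Section 6.3.2 separates one efficacy GEE from the sensitivity analyses, and 6.3.3.1 labels the historical-control models as secondary. The week-52 comparison sits inside the primary analysis section. Restricted to two visits, time and indicator coincide, so it reduces to the mean week-52 change. All of this stands. A reader might infer that the week-52 analysis is missing; it is not. What is open is which of slope, level and week 52 decides.

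The error inflation is conditional. Aiming for efficacy across several approaches can also mean that the results should agree, and that reading does not inflate error. The simulation ignores the bounded 0–11 scale and the possible ceiling that Section 1.5 mentions. So the percentages illustrate the problem; they do not measure this trial. But the plan does not exclude the either-step reading, and 6.3.2 attaches a treatment interpretation to each step.

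On power, both the synopsis and 6.4 do say that the figures concern a paired t-test on averages. What is missing is the sensitivity label in the synopsis, and a basis for carrying the figures over to the primary outcome.

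A reader might also see a conflict in the Abstract, which makes safety as well as efficacy the primary objective. Its next sentence ties efficacy to the week-52 AGS change, so that is not a conflict over the endpoint. The wording in 6.4 is.

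**Conclusion.** The point holds, as something to correct before the analysis rather than a flaw that defeats the design. The endpoint is the week-52 change; the named efficacy analysis tests slope and then level; and no single result is declared decisive. If either step counts, two-sided error is 8.5% to 10.0% with a corrected SE, under the assumed visit pattern, SDs and complete data.

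Two stronger readings are tempting and are not supported. First, that the trial is underpowered or its power miscalculated: the stated figures reproduce, and power for the week-52 change is unknown, not shown to be low. Second, that the raw baseline-to-week-52 change should simply become the sole deciding test: that would drop the pre-treatment trend adjustment which the GEE has. With an assumed gain of 0.25 points per year and no drug effect, the raw test would favour the drug in 14%–38% of trials at n = 30. The documents do not give the size of any natural trend, so this too is a range under assumptions.

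**What to change.** 1. **Section 6.3.2:** name one deciding two-sided 5% test and fix its time coding. Preferably use a week-52 contrast that keeps the pre-treatment trend, such as the model-based departure from that trend at week 52 in the planned GEE. With time in years this is the indicator coefficient plus the interaction coefficient times one. Report the raw week-52 change beside it, not as the sole deciding test. Slope and level become supportive. If both are to carry the claim, use one joint test or 0.025 each. State the standard error to be used; a small-sample correction suits 30 to 45 patients.
2. **Synopsis and 6.4:** state that 98.3% and 80% apply only to the sensitivity paired t-test on averages. Recompute power for the named contrast at n = 30 and n = 45 from its SD in the compassionate-use data.
3. **Section 6.4:** make the AGS scale the primary outcome and safety a secondary one, consistent with 6.1 and 6.2.

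The cost is wording in three places and one power calculation; no new visits are needed. The restated power may be lower than 98.3%. A trend-adjusted contrast is less precise than the raw change, since the pre-treatment trend must itself be estimated. Slope or level alone could no longer support the primary claim without the stated error control.
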